Appendix 3: Regulatory and Ethical Considerations

This investigation will be conducted in accordance with the Clinical Investigation Plan (CIP) and with the following:

- Consensus ethical principles derived from international guidelines including the Declaration of Helsinki and 21 CFR Part 812, 50, 54, 56.
- Applicable International Organization for Standardization (ISO) ISO14155 Clinical investigation of medical devices for human subjects — Good clinical practice, Good Clinical Practice (GCP) Guidelines.

The CIP, CIP amendments, Informed Consent Form (ICF) along with associated information sheets, and other relevant documents must be submitted to an Ethics Committee (EC) by the Investigator and reviewed and approved by the EC and regulatory authority before the investigation is initiated.

Any substantial CIP amendments, likely to affect the safety of the subjects or the conduct of the study, will require EC, IRB, and regulatory authority approval before implementation of changes made to the study design, except for changes necessary to eliminate an immediate hazard to investigation subjects or any non-substantial changes, as defined by regulatory requirements.

Informed Consent for Non-vulnerable Populations

Subjects will be given an opportunity to ask questions about the investigation prior to providing consent for participation. Written documentation of informed consent is required prior to starting the intervention/administering the study product. Consent forms will be IRB-approved, and the subject will be asked to read and review the document. The subject should have the opportunity to discuss the study with their surrogates or think about it prior to agreeing to participate, unless study timeframes do not allow for such discussions. The subjects may withdraw consent at any time throughout the course of the trial.

A copy of the signed informed consent form will be given to the subject, and another will be maintained in the subject's records. The rights and welfare of the subjects will be protected by emphasizing to them that the quality of their medical care will not be adversely affected if they decline to participate in the study.

When informed consent of the subject is not possible because of the subject's medical condition, the informed consent of the legally authorized representative, if present, shall be requested (see the below section on ***Informed Consent for Vulnerable Populations***).

If informed consent is not obtained prior to any research procedures being conducted, the investigative site must notify the Sponsor and IRB within 24 hours of knowledge of the incident.

If new information becomes available, that can significantly affect a subject's future health and medical care, this information shall be provided to the subject(s) affected in written form. If relevant, all affected subjects shall be asked to confirm their continued informed consent in writing.

Informed Consent for Vulnerable Populations

Considering the nature of the clinical investigation as well as the clinical investigation population, is it likely that potential subjects may not be able to give voluntary written informed consent in advance of the procedure (vulnerable individual lacking capacity). A personal legally authorized representative (preferably the nearest relative or healthcare proxy) of the subject shall be consulted in the event the subject is unable to consent for themselves and this person will be the one responsible for assenting to

the subject participation in the clinical investigation. After the procedure is completed, the consent of the subject will be obtained as soon as the subject has recovered capacity. Upon regaining capacity, those subjects who do not wish to consent, may request that all data obtained under the assent be withdrawn from the study database.

Informed Consent for Subjects Unable to Read or Write

Informed consent shall be obtained through a supervised oral process if the subject or legally authorized representative is unable to read or write. An independent witness shall be present throughout the process. The written informed consent form and any other information shall be read aloud and explained to the prospective subject and his/her legally authorized representative and, whenever possible, shall sign and personally date the informed consent form. The witness also signs and personally dates the informed consent form attesting that the information was accurately explained, and that informed consent was freely given.

Disclosure

All information provided regarding the investigation, as well as all information collected and/or documented during the course of the investigation, will be regarded as confidential. The Investigator (or designee) agrees not to disclose such information in any way without prior written permission from the Sponsor.

Appendix 4: Schedule of Assessments**Table 5. Schedule of Antithrombotic and Anticoagulation Management**

Time period	Screening/ preoperative period	Operation	Postoperative day 1	>1 day post- operation	30-day follow- up	
Subjects with ACS or coronary stent placement within the previous 6 months						
Aspirin	X	X	X ^a	X	X	
Ticagrelor/P2Y ₁₂ inhibitor ^b	X ^c		X ^d	X	X	
Thromboprophylaxis		SOC ----- SOC				
All other subjects						
Aspirin	SOC	SOC	SOC	SOC	SOC	
Ticagrelor/P2Y ₁₂ inhibitor ^b	X ^c		SOC-----SOC			
Thromboprophylaxis		SOC ----- SOC				

^aSubjects not previously on Aspirin in the preoperative setting should be initiated on Aspirin therapy at 6 hours post-op, per institutional protocols

^bChoice of agent for postoperative DAPT is at the discretion of the treating physician, in accordance with standard clinical guidelines

^cTiming of last dose must be consistent with the study inclusion criteria

^dResumption of ticagrelor therapy should be within 24hrs post-op if there is no clinical concern for bleeding. Otherwise, if concern for bleeding exists, ticagrelor should be resumed as soon as deemed clinically safe in the judgement of the surgeon. Known benefit of ticagrelor in postoperative graft/stent patency must be weighed against bleeding risks

SOC = per institutional protocols

Table 6: Schedule of Assessments

Study Procedures	Screening	Pre-CPB	Operation	Post-CPB	Post-Operation					Follow-up Visit/End of Study/Early Termination	
Timepoint	Up to 2 days prior to the day of Operation	Within 2 hours before start of operation (i.e., skin incision)	From chest incision to chest closure	Within 30 min after end of CPB	ICU Admission	POD 1	POD 2	POD 3	POD 4	POD 5-29	POD 30 + 5 days
Informed consent/authorization ^a	X										
Inclusion/exclusion criteria	X										
Demographic information	X										
EuroScore II	X										
STS Risk Score	X										
Last pre-operation dose of ticagrelor (date, time, and dosage)	X										
Medication history within 30 days of study enrollment	X ^r										
Physical exam, height, weight ^b	X ^r										
Planned surgical procedure ^c	X										
Drug removal blood sampling ^d		X	X	X							
Medical history	X										
Concomitant medications	X	X	X		X	X	X	X	X	X ^s	X
EKG ^e	X				SOC ^t						
Pregnancy test ^f	X										
Cardiac troponin (cTn) ^g	X				SOC ^t						
Hematology ^g	X				X	X	X ^u	SOC	SOC	SOC	
Clinical chemistry ^g	X				X	X	X ^u	SOC	SOC	SOC	
Coagulation panel ^g	X				X	X	X ^u	SOC	SOC	SOC	
Vital signs ^h	X				SOC	X	X	SOC	SOC	SOC ^s	SOC
CPB duration ⁱ			X								
DrugSorb TM flow rate & flow duration ⁱ			X								
Surgical procedure type ^j			X								
Activated Clotting Time (ACT) ^k			X	X							

Study Procedures	Screening	Pre-CPB	Operation	Post-CPB	Post-Operation					Follow-up Visit/End of Study/Early Termination
	Up to 2 days prior to the day of Operation	Within 2 hours before start of operation (i.e., skin incision)	From chest incision to chest closure	Within 30 min after end of CPB	ICU Admission	POD 1	POD 2	POD 3	POD 4	
Timepoint										
Arterial Blood Gas (ABG) ¹			X	X	X					
Blood products ^m	X				X	X	X	X	X ^s	
Operation blood loss and drainage ^m			X							
Post-Operation chest tube drainage					X-----X					
Post-Op blood loss & bleeding ^m					X	X	X	X	X ^s	X
Daily assessment						X	X	X	X	X ^s
Adverse events ⁿ	X	X	X	X	X	X	X	X	X	X
Ventilation and mechanical support ^o					X	X	X	SOC	SOC	SOC
FiO2 ^p					X	X	X	SOC	SOC	SOC
Vasopressor requirements ^q					X	X	X	SOC	SOC	SOC

Abbreviations: AE = adverse event; CPB = cardiopulmonary bypass; D = day; h = hour; eCRF = electronic case report form; ICF = Informed Consent Form; ICU = Intensive Care Unit; POD = post-operative day; SOC = standard of care.

^a Authorization or informed consent must be obtained at Screening (see Appendix 3)

^b Body mass index will be calculated from the subject's height and weight measurements obtained at Screening or from the values in the medical record in the current hospital admission.

^c Pre-randomization stratification will be performed based on the *planned* surgical procedure, which may differ from the performed procedure.

^d Blood samples will be collected for the determination of plasma ticagrelor concentration at a designated bioanalytical laboratory using a validated assay. The pre-CPB blood sample will be drawn prior to the start of cardiopulmonary bypass and can be up to 2hrs prior to skin incision. The post-CPB blood sample will be drawn as soon as possible following the end of CPB, and no later than 30min after the subject has been disconnected from the CPB circuit. During the procedure, while the subject is on CPB, serial sampling will be obtained q30±15min up through 2hrs of CPB. If the procedure requires a CPB time of <2hrs, then sampling will be q30±15min only up through completion of the CPB.

^e Baseline EKG is required on file within the subject's medical record pre-op but does not need to have been performed within the 2 days prior to the day of surgery. Post-op EKG is only mandated in the event of possible MI

^f In all females of child-bearing potential. Performed in serum. Pre-consent test results done during the current admission MAY be used. Pre-consent test results done before the current admission MAY NOT be used.

^g Refer to Appendix 2 for a list of evaluations in the hematology, clinical chemistry, cardiac biomarker, and coagulation tests. During Screening, if consented subjects enter the Operation Phase without post-consent evaluation of hematology, clinical chemistry, or coagulation tests to record, the last pre-consent laboratory values MAY be used. Post-op cTn is only mandated in the event of possible MI

^h Vital signs include supine blood pressure, pulse rate, respiratory rate, oxygen saturation, and body temperature.

ⁱ Duration of CPB = time from the start of CPB to end of CPB, which may differ from duration of operation. Flow rate and flow duration for the device will be recorded q30±5min while patient is on CPB; flow rates are not mandated while subject is on hypothermic circulatory arrest (HCA).

^j Details regarding the surgical type will be recorded. Delayed sternal closure will be recorded. *Re-exploration/re-thoracotomy will be recorded according to the same schedule as AEs and documented in the re-operation eCRF.*

^k ACT will be obtained once at 30min into CPB ±15min, and once within 30min post-protamine administration (post-CPB). Intraoperative ACT is documented in the ACT log, and not recorded in the

Coagulation Test eCRF.

- ¹ During the operation phase, arterial blood gas analysis will be obtained at the following time periods: within 30min pre-CPB, 30 ± 15min into CPB, within 30min post-CPB, and upon admission to the ICU
- ^m Blood product administration will be monitored and recorded from the point of consent through discharge. Cell Saver will **not** be included as blood product administration. Blood loss and bleeding events will be monitored and recorded through follow-up, and drainage will be monitored from chest closure to 12h post-op (for UDPB class) and continued from 12hr post-op through at least 24h post-operation.
- Measurement of drainage after 24h and through time of chest/mediastinal drain removal will be per SOC.
- ⁿ All AEs will be recorded from point of authorization to participate in the study through the 30-day Follow-up. Serious AEs occurring after 30 days post-operation are to be reported to the Sponsor if, in the judgment of the Investigator, there is concern for potential association between the event and the use of the DrugSorb™-ATR device.
- ^o If subject is intubated/requires mechanical ventilatory support, the maximum ventilation and mechanical support requirements will be recorded for each day.
- ^p Documented in the ABG eCRF; only required if the subject is intubated or on mechanical ventilatory support
- ^q The maximum vasopressor dosage will be recorded each day.
- ^r Physical exam performed on the day of screening as part of standard of care but occurring prior to signing of informed consent *may* be used for the screening PE. The physical exam and medication history will be repeated on the day of the procedure, if the day of the procedure is different than the day of screening
- ^s Assessments completed daily ***through hospital discharge***.
- ^t In the advent of any cardiac ischemic AEs, EKG (to assess for Q waves) and cTn **must** be obtained. EKG will be provided as source documentation for CEC adjudication. cTn will be documented within the laboratory eCRF for CEC event adjudication
- ^u Through postoperative day 2 only.

Appendix 5: Antithrombotic Medications Allowed/Disallowed

Aspirin – allowed

Ticagrelor – allowed

Clopidogrel – any use within 7 days disallowed (as may have confounding effects on bleeding)

Prasugrel – any use within 7 days disallowed (as may have confounding effects on bleeding)

Cangrelor – any use within 4 hours of (or during) the index procedure is disallowed (as may have confounding effects on bleeding)

Argatroban – any use within 4 hours of (or during) the index procedure is disallowed

Bivalirudin – any use within 2 hours of (or during) the index procedure is disallowed

Heparin – allowed

Low molecular weight heparin (e.g., enoxaparin) and fondaparinux – allowed

DOACs (e.g., apixaban, rivaroxaban, dabigatran and edoxaban) – any use within 5 days is disallowed, as it may have confounding effects on bleeding

Warfarin – recent use disallowed unless INR < 1.5 as otherwise may have confounding effects on bleeding

Tirofiban – any use within 8 hours disallowed as may have confounding effects on bleeding (restoration of platelet function normally occurs within approximately 4 hours)¹

Eptifibatide – any use within 8 hours disallowed as may have confounding effects on bleeding (restoration of platelet function normally occurs within approximately 4 hours)¹

Abciximab – any use within 5 days disallowed as may have confounding effects on bleeding (restoration of platelet function normally occurs within approximately 72 hours)¹

References (for this appendix only):

1. Schrör K, Weber AA. Comparative Pharmacology of GP IIb/IIIa Antagonists. *J Thromb Thrombolysis*. 15:71–80.

## List of Abbreviations

ADE	Adverse device effect
AE	Adverse event
AUC	Area under the curve
CABG	Coronary artery bypass grafting
CEC	Clinical Events Committee
CI	Confidence Interval
CIP	Clinical Investigation Plan
CIR	Clinical Investigation Report
CPB	Cardiopulmonary bypass
CTD	Chest tube drainage
DSMB	Data Safety and Monitoring Board
ECG	Electrocardiogram
i-CABG	Isolated coronary artery bypass grafting
ICF	Informed Consent Form
ICH	International Conference on Harmonisation
ICU	Intensive Care Unit
ITT	Intent-to-Treat
mITT	Modified Intent-to-Treat
MedDRA	Medical Dictionary for Regulatory Activities
MI	Myocardial infarction
PK	Pharmacokinetic(s)
PT	Preferred Term
PRBC	Packed red blood cells
SADE	Serious adverse device effect
SAE	Serious adverse event
SaO 2	Oxygen saturation
SAP	Statistical Analysis Plan
SD	Standard deviation
SoC	Standard of Care
SOC	System Organ Class
STAR-T	Safe and timely antithrombotic removal - ticagrelor
TEAE	Treatment-emergent adverse event
UADE	Unanticipated adverse device effect
UDPB	Universal Definition of Perioperative Bleeding

## 1 INTRODUCTION

This statistical analysis plan (SAP) describes the statistical methods and data presentation to be used for analyzing and reporting effectiveness and safety data for study Safe and Timely Antithrombotic Removal – Ticagrelor (STAR-T). This document has been prepared based on the Clinical Investigation Plan (CIP) number 2021-01 (Version 5.1, dated: 27-May-2023).

[figure not shown]
This SAP will be finalized as of the full execution (signatures) of this document. Any additional analyses (*post hoc*), or changes to the planned analyses as described in this SAP will be identified and documented in the Clinical Investigation Report (CIR).

### 1.1. Study Objectives

- To demonstrate reductions in postoperative bleeding with the intraoperative use of DrugSorb™-ATR in patients undergoing cardiothoracic surgery with CPB within two days of ticagrelor discontinuation
- To demonstrate reductions in ticagrelor blood levels  $\Delta[\text{ticagrelor}]$  with the intraoperative use of DrugSorb™-ATR
- To establish safety of the intraoperative use of DrugSorb™-ATR in the intended population

### 1.2. Study Design

This is a prospective, multi-center, randomized, double-blind clinical study. Subjects will be randomized in a 1:1 ratio to either standard of care (SoC) or standard of care plus intraoperative treatment with the DrugSorb™-ATR device. The subjects will go through the 6 investigational phases as shown below:

\* Pre-CPB phase may overlap with the Screening Phase.

### 1.3. Study Endpoints

#### 1.3.1. Primary Effectiveness Endpoint

Ranked composite of perioperative bleeding events:

- (1) Fatal perioperative bleeding (occurring within 48hrs post-index procedure),
- (2) UDPB  $\geq 2$  (moderate, severe, or massive) perioperative bleeding,
- (3) 24-hour chest tube drainage volume (mL)

**1.3.1.2. Supplementary Composite Effectiveness Endpoint**

Ranked composite of perioperative bleeding events:

- (1) Fatal perioperative bleeding (occurring within 48hrs post-index procedure),
- (2) UDPB  $\geq 3$  (severe or massive) perioperative bleeding,
- (3) 24-hour chest tube drainage volume (mL)

is proposed to evaluate the treatment effect on the more severe bleeding events.

**1.3.2. Key Secondary Effectiveness Endpoint**

Percent difference in pre-CPB vs. post-CPB blood ticagrelor levels as measured by liquid chromatography/tandem mass spectrometry (LC/MS-MS)

**1.3.3. Additional Secondary Effectiveness Endpoints**

- 24-hour chest tube drainage volume
- Total platelet transfusions from end of operation through the duration of the index hospitalization (volume and units)
- Total PRBC transfusions from end of operation through the duration of the index hospitalization (volume and units)
- Total UDPB events (by class)
- All surgical re-exploration for excessive bleeding
- Total fatal perioperative bleeding events

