Additional powered secondary endpoints include 24-hour CTD (volume [mL]), total platelet transfusions (volume [mL] and units), and total PRBC transfusions (volume [mL] and units) during the index hospitalization. Twenty-four-hour CTD (mL) will be assessed via two-sample t-test for mean difference. The transfusion endpoints will all be analyzed using two-sample t-tests for mean differences, and Fisher-Freeman-Halton exact tests for units. In the event the assumptions for a two-sample t-test are not met in any of the above, a nonparametric test such as a Mann-Whitney test will be employed, with median and range values provided in the output. Other secondary endpoints include the remaining Win Ratio component parts: proportions of fatal perioperative bleeding events will be assessed via Fisher's exact test; and proportions of UDPB events (by category) will be assessed via a Fisher-Freeman-Halton exact test. The secondary endpoint of surgical re-exploration for bleeding will take into account time to re-exploration.

Sample Size

Up to 140 subjects will be randomized in a 1:1 ratio to the treatment and control arms. Sample size is based on assumed response rates for the primary effectiveness Win Ratio sub-components, and can be calculated via an iterative simulation process with programming code available in an appendix to Redfors et al. (2019).[11] With a Finkelstein-Schoenfeld test, total of 57 subjects per arm ensures power of $\geq 99.7\%$, using a two-sided alpha (α) of 0.05. With this same per arm sample size, power for the key secondary endpoint is estimated at $>99.9\%$, and for 24-hour chest tube drainage (mL), $>99.9\%$, based on a two-sample t-test assuming equal variance and a two-sided alpha of 0.05. Similarly, although assuming unequal variances, power for comparisons of platelet transfusions (volume [mL]) and PRBC transfusions (volume [mL]), is estimated at 98.0% and 96.7%, respectively.

Analysis Populations

Enrolled subjects include all subjects who provide informed assent/consent. Enrolled subjects who do not meet criteria for study eligibility are screening failures and will exit the study.

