Benchtop studies of drug removal by the DrugSorb™-ATR device (CytoSorbents, unpublished data) demonstrate concentration and time dependent absolute drug removal. Based on these benchtop studies, a conservative estimate of 40% reduction in blood concentration of ticagrelor between pre- and post- DrugSorb™-ATR removal is expected, with a standard deviation of 40%, in the treatment arm. Minimal change is expected in the control arm. A two-sample t-test will be used to evaluate the difference between treatment arms. Due to highly variable baseline ticagrelor blood levels in the above benchtop studies, percent change from baseline will be analyzed as opposed to observed values. We anticipate drug removal data from other clinical studies in this application to become available during the course of the study and we plan to update the above assumption if necessary based on *in vivo* data.

Additional powered secondary endpoints include 24-hour CTD (volume [mL]), total platelet transfusions during the index hospitalization (volume [mL] and units), and total PRBC transfusions during the index hospitalization (volume [mL] and units). Twenty-four-hour CTD (mL) will be assessed via two-sample t-test for mean difference. In the event the assumptions for a two-sample t-test are not met, a nonparametric test such as a Mann-Whitney test will be employed, with median and range values provided in the output. The transfusion endpoints will all be analyzed using two-sample t-tests for mean differences, and Fisher-Freeman-Halton exact tests for units. In the event the assumptions for a two-sample t-test are not met, a nonparametric test such as a Mann-Whitney test will be employed, with median and range values provided in the output. Other secondary endpoints include the remaining Win Ratio component parts: proportions of fatal perioperative bleeding events will be assessed via Fisher’s exact test; and proportions of UDPB events (by category) will be

assessed via a Fisher-Freeman-Halton exact test. All surgical re-exploration for excessive bleeding, including those events occurring beyond the timeframe captured within the UDPB component of the primary endpoint will be captured as a secondary endpoint. Time to re-exploration will be taken into account.

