Type I error (alpha, α) will be preserved from inflation due to multiplicity across the primary effectiveness, key secondary, and secondary endpoints via a hierarchical closed testing step-down approach. Only in the event that preceding endpoints are declared statistically significant at the alpha 0.05 level, can further endpoints also be declared significant. The order of hierarchical testing will follow the order of primary, key secondary, and secondary endpoints as listed in the paragraph above, namely: the primary endpoint will be tested first, followed by the key secondary endpoint (percent change in pre-CPB vs. post-CPB blood ticagrelor levels), followed by the first secondary endpoint (24-hour CTD), second secondary endpoint (platelet transfusions), and lastly (PRBC transfusions). Should all preceding statistical comparisons show results below their alpha cut-off values, further secondary endpoints will be evaluated: the proportion of fatal perioperative bleeding events, proportions of UDPB events (by category), and surgical re-exploration rates.

Other exploratory endpoints include:

- Area under the concentration time curve (AUC), using the trapezoidal approach, for intraoperative ticagrelor pharmacokinetic (PK) concentration
- Operative time (measured from start of skin incision to completion of chest closure)
- Duration of ICU stay
- Duration of hospital stay
- 30-day hospital re-admissions

Details on methods of analysis for exploratory endpoints will be provided in the SAP.

Further details regarding summary and analysis of effectiveness data will be provided in the SAP.

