##### **5.4.2.3 Other Categorical Secondary Effectiveness Endpoints**

The following endpoints associated with the bleeding events will be evaluated within 48 hours after the index surgery and adjudicated by CECs according to the CEC charter.

- All surgical re-exploration for excessive bleeding
- Total fatal perioperative bleeding events

The adjudicated endpoints will be analyzed using the Fisher exact test to evaluate the risk of having the events between the treatment groups. The estimated rates within each group and odd ratios comparing the treatment groups will be provided along with the 95% confidence intervals.

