#### **5.4.3 Time-to-event Analysis for the Secondary Effectiveness Endpoints**

Time-to-event analysis may be applied to the events of interest, along with Kaplan-Meier plot by treatment when deemed appropriate.

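### The SAP narrows the windows of three endpoints in its testing sequence relative to the protocol without declaring it: re-exploration stops at 48 hours, and platelet and PRBC totals start at end of operation

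*SAP*

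**What the plan says.** **Transfusions.** Protocol 4.3.3 and 11.3 define the platelet and PRBC endpoints as totals during the index hospitalization and give no later starting point. SAP 1.3.3 has "Total platelet transfusions from end of operation through the duration of the index hospitalization (volume and units"), and the same window for PRBC. SAP 5.4.1.2 repeats that window in the analysis. Its supplemental analysis changes the measure from volume to units but keeps the window.

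**Re-exploration.** Protocol 11.3 covers all re-explorations for excessive bleeding. Its wording on scope is "including those events occurring beyond the timeframe captured within the UDPB component of the primary endpoint will be captured as a secondary endpoint", and it adds "Time to re-exploration will be taken into account". The protocol synopsis agrees: "The secondary endpoint of surgical re-exploration for bleeding will take into account time to re-exploration". SAP 1.3.3 keeps the name "All surgical re-exploration for excessive bleeding". SAP 5.4.2.3, which covers re-exploration and fatal bleeding, says "The following endpoints associated with the bleeding events will be evaluated within 48 hours after the index surgery". SAP 5.4.3 says "Time-to-event analysis may be applied to the events of interest".

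**Status of these endpoints.** SAP 3.7 and 5.1 put all three in the fixed sequence. SAP 1 states that the SAP was prepared from CIP version 5.1. The SAP's contents list has no section on changes from the protocol.

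**The concern.** The narrower windows are printed openly, but the available SAP text neither identifies nor justifies them as departures from the protocol. An analyst who follows the SAP will test three endpoints that differ from those the protocol defines. A significant result could not be read as a result on the protocol endpoint.

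Two kinds of patient show the difference:

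- A patient taken back for bleeding after 48 hours is scored as having no event, in an endpoint whose name says every re-exploration counts.
- A patient given platelets after bypass ends, when device treatment is complete, but before the chest is closed, and none later, is scored as not transfused.

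The platelet and PRBC endpoints are among the secondary endpoints for which the protocol claims power, so they are part of the confirmatory case.

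**Working it through.** **1. Windows side by side**

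| Endpoint | Protocol | SAP | Position in SAP 3.7 |
|---|---|---|---|
| Platelet total | Index hospitalization (4.3.3, 11.3) | End of operation to discharge (1.3.3, 5.4.1.2) | 4 |
| PRBC total | Index hospitalization (4.3.3, 11.3) | End of operation to discharge (1.3.3, 5.4.1.2) | 5 |
| Re-exploration | All, including those after the UDPB timeframe; no upper limit (11.3) | Within 48 hours (5.4.2.3) | 7 |

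The SAP sequence is: primary, key secondary, 24-hour CTD, platelets, PRBC, UDPB by class, re-exploration, fatal bleeding. That is 8 tests, 3 of them with a narrowed window.

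**2. Units that drop out.** Protocol 9.1 ends the operation phase at chest closure, and SAP 1.3.4 measures operative time to the same point. Protocol 9.2.1 leaves platelets and PRBC given before closure out of the UDPB class and the primary endpoint, but states no such exclusion for the secondary totals. Under the SAP, units given between the end of CPB and closure are therefore counted in neither the primary nor the secondary endpoints.

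**3. What the 48-hour limit removes.** Protocol 3 places the UDPB criteria in surgery and the first postoperative day. A 48-hour window reaches past that, so the protocol wording is met in part. Events after 48 hours are lost. The protocol's reason for a 48-hour limit, in section 3, is given for fatal bleeding only. SAP 6.4 reports adjudicated bleeding to 30 days, but descriptively and not as re-exploration.

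**4. The test itself is not in conflict.** The step-down in protocol 11.3 ends with "proportions of UDPB events (by category), and surgical re-exploration rates", so Fisher's exact test on rates is compatible. The mismatch is the window, and the change from a firm commitment on time to re-exploration to an optional analysis.

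**5. The plan's own power figures.** Protocol 11.1 assumes 0.32 (SD 0.9) vs 1.6 (SD 2.2) platelet units and 1.3 (SD 2.1) vs 4.4 (SD 5.7) PRBC units, with 57 per arm and an unequal-variance t-test at two-sided 0.05. The noncentrality is the difference divided by √(SD₁²/n + SD₂²/n).

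- Platelets: 1.28 / √(0.81/57 + 4.84/57) = 1.28 / 0.315 = 4.07; power 98.0% (stated 98.0%).
- PRBC: 3.1 / √(4.41/57 + 32.49/57) = 3.1 / 0.805 = 3.85; power 96.7% (stated 96.7%).

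Both reproduce. The documents do not say what share of units is given before closure, so power under the SAP window cannot be derived. If means and SDs shrank in the same proportion, power would not change.

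**6. How much one patient can matter.** At 65 per arm (SAP 2), one reclassified patient is 1/65 = 1.5 percentage points. The documents give no re-exploration counts. The counts below are assumptions, tested with the two-sided Fisher's exact test:

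| Treatment vs control | p | One control event fewer | p |
|---|---|---|---|
| 0 vs 6 | 0.028 | 0 vs 5 | 0.058 |
| 3 vs 11 | 0.045 | 3 vs 10 | 0.076 |
| 2 vs 6 | 0.27 | 2 vs 5 | 0.44 |

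Near the 0.05 boundary one late event decides the test. Away from it, one event changes nothing.

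**The case against.** The best case for the SAP is that it sensibly refines loosely worded endpoints.

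- **Transfusions.** The trial is about postoperative bleeding, and UDPB already counts these products from chest closure. A literal whole-stay total includes units given before or during bypass, which the device cannot affect. This is a good reason to prefer the SAP window. It is not a declaration of the change, and the SAP does not give it.
- **Meaning of end of operation.** The cited sections define a study phase and operative time, not this term, and delayed sternal closure could separate the two moments. The SAP should therefore define the term, but both documents do end the operation at closure.
- **Re-exploration.** The protocol sets no upper limit, so the SAP has to choose one, and 48 hours does pass the UDPB timeframe. The protocol also names no method for taking time into account. Both points stand. They do not reconcile a 48-hour cut with an endpoint that the SAP itself still names as all re-explorations.
- **CEC charter.** It was not available and may set a window. It would not make the protocol and SAP texts agree.
- **Size.** Protocol 3 reports that most major bleeding in the cited trial population fell within 24 hours of surgery, so late events are probably few. Position 7 is formally tested only after six earlier successes. Any binary endpoint near p = 0.05 can turn on one patient. This limits the practical weight of the re-exploration part.

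**Conclusion.** The concern holds and should be fixed. Three of the eight tests in the SAP's sequence use narrower windows than the protocol, with no declaration or justification in the available SAP text. On re-exploration the SAP also contradicts its own endpoint list.

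The numerical effect is unknown. The documents give neither the share of units transfused before closure nor the share of re-explorations after 48 hours. The re-exploration effect may well be small; the transfusion effect cannot be judged. The Fisher results rest on assumed counts and show only that one patient can matter near the boundary. The primary endpoint and its power are not affected, and no bias, type I error inflation or power loss is claimed. What is at stake is whether a significant secondary result can be attributed to the endpoint the protocol defines.

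The conclusion assumes that the SAP's title and signature pages, which were not available, contain no note on these windows.

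**What to change.** Make these changes before unblinding.

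1. **SAP 5.4.2.3:** apply the 48-hour limit to fatal bleeding only. Count all recorded re-explorations for excessive bleeding and state where the window ends. The protocol sets no limit; data are recorded to the 30-day follow-up. Keep Fisher's exact test on rates.
2. **SAP 5.4.3:** replace the optional wording with a definite analysis of time to re-exploration.
3. **SAP 1.3.3 and 5.4.1.2:** choose one of two routes. Either test the index-hospitalization totals and keep the from-end-of-operation totals as supplementary, or keep the SAP window, declare and justify it as a change from the CIP, and report the protocol totals alongside. In either case, define end of operation.

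The cost is SAP wording and programming. No new data are needed: Table 6 in protocol Appendix 4 records blood products from consent through discharge (footnote m) and re-explorations on the adverse-event schedule to the 30-day follow-up (footnotes j and n). There are two downsides. The wider transfusion window adds units given before or during bypass, which the device cannot affect. Late re-explorations may follow the restart of antithrombotic therapy.
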